Both study drug and placebo will be dispensed by the BWH Investigation Drug Service in 3-month allotments either in person at the screening visit, other non-study related office visit at BWH, or directly to the patient within 2 business days of the enrollment visit via mail or courier in accordance with BWH Investigation Drug Service policy. Subsequent allotments will be dispensed via mail or courier in accordance with BWH Investigation Drug Service policy. Our Research Nurse will communicate with study subjects by telephone at 3 months intervals in advance of releasing a 3-month allotment of study drug or placebo to ensure that treatment is not interrupted due to the subjects' supplies running out.

Randomization

Subjects who are 18 years of age or older with provoked DVT and/or PE, have completed at least 3 months of therapeutic anticoagulation, have a low risk of bleeding, and have at least one persistent provoking risk factor will be randomly assigned by computer in a 1:1 ratio to receive apixaban 2.5 mg orally twice daily or oral placebo for extended secondary prevention of VTE for a duration of 12 months.

Safety Outcomes

Primary Safety Outcome

The primary safety outcome will be major bleeding at 12 months. Major bleeding is defined as overt bleeding that is associated with a decrease in the hemoglobin level \geq 2 g/dL, leads to transfusion \geq 2 units of packed red blood cells, occurs in a critical site, or contributes to death (27). The primary safety outcome will be independently adjudicated by a blinded Clinical Endpoints Committee (CEC) review.

Secondary Safety Outcome

Clinically relevant non-major bleeding at 12 months will be evaluated (please see below) and is defined as overt bleeding that does not meet the criteria for major bleeding but that is associated with the need for medical intervention, unscheduled contact with a physician, interruption or discontinuation of the study drug, or discomfort or impairment of activities of daily living (28).

Efficacy Outcomes

Primary Efficacy Outcome

The primary efficacy outcome will be symptomatic, recurrent VTE, defined as the composite of deep vein thrombosis and/or pulmonary embolism at 12 months. The primary efficacy outcome will be independently adjudicated by a blinded CEC review.

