Routine laboratory testing is neither recommended nor required in patients receiving extended duration apixaban, including the 2.5 mg twice daily dosing regimen. Patients enrolled in the study will either have been identified from one of the practices of our Vascular Medicine faculty or will be assigned to one of our faculty for long-term management of VTE. Accordingly, every patient enrolled in the study will have ongoing medical care with a dedicated Vascular Medicine provider. Study patients will be encouraged to follow-up with their primary care, , and other appropriate clinicians. Specifically, at the end of the treatment visit, every patient will be reminded to follow-up with a PCP as dictated by routine care and best clinical practice. Demographic, clinical characteristics, medication records, and outcomes will be abstracted from the BWH Electronic Health Record (EPIC).

When our Research Nurse conducts the every 3-month telephone call in advance of releasing a 3-month allotment of study drug or placebo the subject will be queried for any issues with the study or adverse events.

We will conduct an end-of-treatment visit to obtain data relevant to the study end points.

We will assess medication adherence via pill count. Medication adherence will be calculated in three month intervals as the total number of doses taken divided by the total number of doses prescribed for that time period ($[x / 180] \times 100$ = medication adherence [%]) and also for the total 360-day study period ($[x / 720] \times 100$ = medication adherence [%]). Subjects will be given a study drug diary to fill out at home each day. Subjects will write down the time they take their study drug and any side effects. The study drug diary will be collected at a regularly scheduled office visit or the end-of-treatment visit at conclusion of the study period.

Subject Retention, Withdrawal, and Termination

Continued participation of study subjects will be encouraged at the time of outpatient evaluation through the 12-month follow-up interval. However, study subjects will be informed that they retain the right to withdraw from the study at any time without compromise to their current or subsequent medical care. Subjects will be terminated from the study if they expire or elect to withdraw.

If study subjects elect to withdraw, they will be asked for permission to do the following:

1. Be contacted by telephone **AND**
2. Have their physicians contacted

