Withdrawal criteria will include:

1. Patient requests to withdraw
2. Reasons related to SAE:
 - a. Initiating or continuing study drug places the subject at undue hazard as determined by the Investigator;
 - b. SAE or other safety concern that is related to study drug treatment;
 - c. Major or life-threatening bleeding (as defined in the protocol)
 - d. ALT or AST ≥ 3 ULN, if suspected to be due to the study drug
 - e. Calculated CrCL decreased to < 30 mL/min confirmed by repeat testing at least one week later, or need for dialysis
3. Pregnancy
4. Patient develops severe hepatic impairment (Child-Pugh class C) during the trial
5. Death
6. Lost to follow-up (every attempt will be made by the Investigator not to have subjects “lost to follow-up”)
7. Study terminated by sponsor (termination of all or part of the study by the sponsor, in concert with the study leadership)

Safety Monitor

An independent Safety Monitor has been selected for this study. The Safety Monitor is an expert in VTE and is distinct from the DMSB and Study Staff and will be available throughout the study to assess patient safety issues that may arise, objectively. The Safety Monitor will have the ability to break the blind of a study patient as the need arises (immediately, in real-time). If the Safety Monitor is unavailable because of travel, one of the Physician Study Investigators will serve as back-up. The Safety Monitor will attend DSMB meetings, although will be non-voting. The Safety Monitor will have the ability to request an ad hoc DSMB meeting should a safety issue arise that warrants further review.

Assessment and Reporting of Adverse Events

Definitions

Adverse events

An adverse event (AE) is defined as any new untoward medical occurrence or worsening of a pre-existing medical condition in a patient or clinical investigation subject administered an investigational (medicinal) product and that does not necessarily have a causal relationship with this treatment. An AE can therefore be any unfavorable and unintended sign (including an abnormal laboratory finding, for example), symptom, or disease temporally associated with the use of investigational product, whether or not considered related to the investigational product. The causal relationship to study drug is determined by a physician and should be used to assess all AEs.

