When our Research Nurse conducts the every 3 month telephone call in advance of releasing a 3-month allotment of study drug or placebo the subject will be queried for any issues with the study or adverse events. The Electronic Health Record, Epic, will notify study staff when a study subject is admitted to the hospital or presents to the Emergency Department. This notification will be an additional avenue for detection of SAEs. Providers will also be able to see that the patient is enrolled in the study and how to contact study staff through the EHR.

SAEs will be detected via report from the study subject, the subject's care providers, a study physician or staff member, or identification from the EHR during data collection. Patients that report AEs to the study staff will be contacted by a study physician and triaged to the appropriate setting for care depending on the nature and severity of the AE and in accordance with best clinical practices.

The investigator should report any SAE occurring after these time periods that is believed to be related to study drug or protocol-specified procedure. An SAE report should be completed for any event where doubt exists regarding its status of seriousness. If the investigator believes that an SAE is not related to study drug, but is potentially related to the conditions of the study (such as withdrawal of previous therapy, or a complication of a study procedure), the relationship should be specified in the narrative section of the SAE Report Form.

SAEs, whether related or unrelated to the study drug, and pregnancies must be reported to BMS within 1 business day of becoming aware of the event:

SAE Email Address: [contact]

SAE [contact]

SAEs must be recorded on the FDA MedWatch Form 3500A. Pregnancies must be reported on a Pregnancy Surveillance Form.

If only limited information is initially available, follow-up reports are required. (Note: Follow-up SAE reports should include the same investigator term(s) initially reported.)

If an ongoing SAE changes in its intensity or relationship to study drug or if new information becomes available, a follow-up SAE report should be sent within 24 hours to the BMS (or designee) using the same procedure used for transmitting the initial SAE report. All SAEs should be followed to resolution or stabilization.

SAE Reconciliation

The Sponsor will reconcile the clinical database AE cases (**case level only**) transmitted to BMS Global Pharmacovigilance (GPV&E) ([contact]).

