 - ✓ Other important findings which may be reported by BMS as an Expedited Safety Report (ESR) include: increased frequency of a clinically significant expected SAE, an SAE considered associated with study procedures that could modify the conduct of the study, lack of efficacy that poses significant hazard to study subjects, clinically significant safety finding from a nonclinical (eg, animal) study, important safety recommendations from a

study data monitoring committee, or sponsor or BMS decision to end or temporarily halt a clinical study for safety reasons.

- ✓ Upon receiving an ESR from BMS, the investigator must review and retain the ESR with the IB. Where required by local regulations or when there is a central IRB/Independent Ethics Committee (IEC) for the study, the sponsor will submit the ESR to the appropriate IRB/IEC. The investigator and IRB/IEC will determine if the informed consent requires revision. The investigator should also comply with the IRB/IEC procedures for reporting any other safety information.

Non-Serious Adverse Events

A non-serious adverse event (NSAE) is an AE not classified as serious.

Non-Serious Event Collecting and Reporting

The collection of non-serious AE information should begin following the subject's written consent to participate in the study. All non-serious adverse events (not only those deemed to be treatment-related) should be collected continuously during the treatment period and for a minimum of 30 days following the last dose of study treatment.

Non-serious AEs should be followed to resolution or stabilization, or reported as SAEs if they become serious. Follow-up is also required for non-serious AEs that cause interruption or discontinuation of study drug and for those present at the end of study treatment as appropriate.

Non-serious Adverse Events (AE) are to be provided to BMS in aggregate via interim or final study reports as specified in the agreement or, if a regulatory requirement [eg, IND US trial] as part of an annual reporting requirement.

Laboratory Test Abnormalities

All laboratory test results captured as part of the study should be recorded following institutional procedures. Test results that constitute SAEs should be documented and reported to BMS as such.

The following laboratory abnormalities should be captured and reported as appropriate:

- Any laboratory test result that is clinically significant or meets the definition of an SAE

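### Nothing ties a check of creatinine and liver results already on file to the month 3, 6 and 9 drug releases; a record look-up would be a cheap safety improvement

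*Combined protocol and SAP*

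**What the plan says.** All references are to the final protocol (11/19/2021).

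**Withdrawal criteria** (Subject Retention, Withdrawal, and Termination). Criterion 2e is "Calculated CrCL decreased to < 30 mL/min confirmed by repeat testing at least one week later, or need for dialysis". Criterion 2d is "ALT or AST ≥ 3 ULN, if suspected to be due to the study drug". Criterion 2a lets the investigator withdraw anyone for whom continuing the drug is an undue hazard.

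**Drug release.** The Study Subject Contact Calendar has a nurse check-in at months 3, 6 and 9, each with a further three months of drug. Treatment Description gives the purpose of the call as "to ensure that treatment is not interrupted due to" supplies running out. Follow-Up Evaluation says that on the call "the subject will be queried for any issues with the study or adverse events". Drug Accountability adds container return and a count at each three-month interval.

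**Laboratory testing.** Follow-Up Evaluation, Feasibility and During Follow-Up all state that no routine on-treatment laboratory tests are required. The Protocol Summary places record review at 12 months.

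**Other routes for a result to reach the study.**
- The automatic Epic alert "will notify study staff when a study subject is admitted to the hospital or presents to the Emergency Department".
- Serious events may also be found through the subject, care providers, "a study physician or staff member, or identification from the EHR during data collection".
- In Follow-Up Evaluation, "every patient enrolled in the study will have ongoing medical care with a dedicated Vascular Medicine provider".
- Laboratory Test Abnormalities asks for capture of "Any laboratory test result that is clinically significant or meets the definition of an SAE".

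**Renal limits at entry.** Study Exclusion Criteria exclude creatinine above 2.5 mg/dL or Cockcroft-Gault CrCl below 25 mL/min. The exclusion checklist in the Case Report Form has the creatinine limit but not the CrCl limit.

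**The concern.** Neither criterion acts on its own. A first CrCl below 30 mL/min has to prompt a repeat at least a week later, and a raised ALT or AST has to prompt a causality judgement. A patient without symptoms may not know of either result, so an open question on the telephone may not bring it out. The protocol can therefore be followed to the letter while another 180 doses of blinded drug are sent to a patient whose qualifying result is in the hospital's own record and has not been looked at by the study. Criterion 2a helps only once the investigator has seen the result.

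The patients most concerned are foreseeable, since an eGFR below 60 is a qualifying risk factor. For them the renal text has a second weakness. Entry is allowed at CrCl 25-29, below the withdrawal value of 30, and the criterion's reference to a decrease does not settle whether such a patient already meets it. What is at stake is individual patient safety. No primary or secondary outcome is laboratory-based.

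**Working it through.** **Doses.** Follow-Up Evaluation uses denominators of 180 doses per three-month interval and 720 for the 360-day course. Both reproduce: 2 x 90 = 180 and 2 x 360 = 720. The releases at months 3, 6 and 9 carry 3 x 180 = 540 doses, and 540 / 720 = 75%. The one-week minimum before a repeat CrCl spans at least 2 x 7 = 14 doses. With a look-up at each release, a filed result waits at most about one allotment (180 doses) before review. The protocol now states no limit.

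**Number of releases.** The sample-size section gives 279 per arm (6% versus 1.5%, two-sided 0.05, 80% power), which reproduces with power 0.8005, and recruits 600 to allow for losses.
- Full retention: 600 x 3 = 1,800 releases, about 300 x 3 = 900 of them apixaban.
- All of the allowance lost before month 3: 2 x 279 = 558, and 558 x 3 = 1,674.

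These are occasions for a check, not releases at risk.

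**Is any check tied to release?** The provisions side by side:

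| Provision | What sets it off | Tied to release? |
|---|---|---|
| Nurse call | Each release | Yes, but open question only |
| Drug accountability | Container return | Yes, but pill count only |
| Epic alert | Admission or ED visit | No |
| Treating provider or staff report | Someone notices and reports | No |
| Adverse event and laboratory capture | Result becomes known to the study | No |
| Liver events of special interest | Case is known or suspected | No |
| Reassessment of pre-existing conditions | No stated time | No |
| Monthly data review, three-monthly DSMB | Data already collected | No |
| Month-12 record review | End of follow-up | No |

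No row requires a look at creatinine, ALT or AST before drug is sent, or a decision to release or hold while a result is unresolved.

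**Entry limits.** Cockcroft-Gault for an illustrative woman of 75 years and 70 kg: (140 - 75) x 70 x 0.85 / 72 = 53.7, so CrCl = 53.7 / creatinine.
- CrCl 30 at 53.7 / 30 = 1.79 mg/dL.
- CrCl 25 at 53.7 / 25 = 2.15 mg/dL.
- At the form's limit of 2.5 mg/dL, CrCl = 53.7 / 2.5 = 21.5.

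So creatinine of about 2.15-2.5 mg/dL passes the form's creatinine check in a patient whose CrCl (about 21-25) the protocol excludes. Creatinine of 1.79-2.15 mg/dL gives an eligible patient who starts below the 2e value.

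**Nurse time**, assuming 3-5 minutes per look-up: 1,674 x 3 / 60 = 83.7 hours to 1,800 x 5 / 60 = 150 hours. Releases fall between study month 3 and month 20 + 9 = 29, which is 26 months: 83.7 / 26 = 3.2 to 150 / 26 = 5.8 hours a month.

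**The case against.** The strongest reply is that follow-up without laboratory tests is a reasoned choice: During Follow-Up states that apixaban needs no routine toxicity monitoring. The result in question was ordered by a clinician, who can see in the record that the patient is enrolled and how to reach the study. An abnormal laboratory finding can be an adverse event, and non-serious events are collected continuously. Pre-existing conditions are to be reassessed, which covers kidney disease. Liver test abnormalities are events of special interest. Criteria 2d and 2e are listed under reasons related to SAEs, so the SAE detection routes apply to them.

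Most of this stands. The choice is legitimate and needs no change, and these routes make a missed result less likely. They do not put a check before the drug leaves the pharmacy.

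A reader might infer that a patient could take all 720 doses after a qualifying result. The documents do not support that. The result would have to predate the first dose, and recent laboratory data are reviewed at screening. The releases at issue carry 540 doses, and reaching even that figure requires every other route to fail.

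On the form, investigators must confirm every protocol exclusion whatever the checklist prints. The supplied form also breaks off partway, so an entry-CrCl field may exist elsewhere. The mismatch between checklist and protocol remains.

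**Conclusion.** The gap is real and small. Two withdrawal criteria depend on laboratory values, and no review of results already on file is linked to the three releases that carry 75% of the doses. Closing it is a cheap patient-safety improvement. The number of patients affected cannot be estimated: the documents give no share with chronic kidney disease, no frequency of routine testing and no rate of crossing either limit. Sample size and power do not change.

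Two stronger readings go too far. A reader might infer that 2d and 2e cannot operate, or that the lack of scheduled tests is an error; the existing routes and the stated rationale answer both. A reader might also infer bias in the trial's outcomes; nothing in the documents shows it.

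The ambiguity of 2e for patients entering at CrCl 25-29, and the CrCl exclusion missing from the form's checklist, are wording defects that stand on the text alone. The creatinine figures rest on one illustrative patient, and the time cost on an assumed 3-5 minutes per look-up. Confidence is medium.

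**What to change.** **Follow-Up Evaluation**, after the sentence on the three-monthly call, add: before the month 3, 6 and 9 releases the research nurse checks the EHR for routine-care creatinine, ALT and AST since the last release, calculates CrCl as at screening, and records values and dates. Any CrCl < 30 mL/min or ALT/AST >= 3 ULN goes to the investigator before release. The investigator arranges the 2e repeat or makes the 2d causality judgement, and documents the decision to release or hold.

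**Withdrawal criteria**, state how 2e applies to patients who enter at CrCl 25-29: for example, any confirmed fall from the entry value goes to the investigator for a withdrawal decision, with need for dialysis unchanged. A new withdrawal limit of 25 for this group is not advised. It has no basis in the documents and would loosen protection for those with the worst renal function. Clinical leads should settle the wording.

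**eCRF**, add the CrCl < 25 mL/min exclusion to the checklist and a field for entry CrCl.

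**Cost.** No added visits, staff or routine blood draws. About 84-150 nurse-hours in total (3.2-5.8 a month), some added data entry, and occasional repeat tests whose number cannot be estimated. Patients who are never tested, or are tested outside the hospital's record, remain unmeasured.
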